**Table 11 Examples of Clinical Ocular AE: Keratopathy**

Example 1	Baseline (CC)	New VA (CC)	Lines VA Change	VA Grade	Clinical Ocular AE Grade
OD	20/20	20/50	(4)	3	Grade 3
OS	20/40	20/70	(3)	2	

Example 2	Baseline (SC)	New VA (SC)	Lines VA Change	VA Grade	Clinical Ocular AE Grade
OD	20/60	20/125	(4)	3	Grade 3
OS	20/100	20/200	(2)	4	

Example 3	Baseline (CC)	New VA (CC)	Lines VA Change	VA Grade	Clinical Ocular AE Grade
OD	20/30	20/80	(5)	3	Grade 4
OS	20/60	20/200	(5)	4	

**5.6.5.2.1 Treatment Guidelines for Clinical Ocular Toxicities**

Corneal Clinical Ocular AEs

- If Clinical Ocular AE is Grade 3, Medical Monitor will be consulted for treatment decision.
- If Clinical Ocular AE is Grade 4, subject will be permanently discontinued from study treatment.

Non-corneal Related Clinical Ocular AEs

- Clinical Ocular AEs other than ocular surface disease/keratopathy in nature, **irrespective of the grade, must be discussed with the Medical Monitor before the subsequent dose (per axitinib product label, patients treated with this product experienced both retinal artery and retinal vein occlusions. Please see product label for details).**
- If the subject develops a need or is recommended to have cataract surgery while on treatment in the study, discuss each case with the Medical Monitor.

**Table 12 Visual Acuity Grading Chart**

Baseline vision (with or without correction, based on patient's daily functional distance vision)	Grade 1* (no change in vision from baseline)	Grade 2 (delta vision change = Number of line change in vision from baseline)	Grade 3 (delta vision change = Number of line change in vision from baseline)	Grade 4 (delta vision change = Number of line change in vision from baseline)
20/20	20/20	20/25 (1) 20/30 (2) 20/40 (3)	20/50 (4) 20/60 (5) 20/70 (6) 20/80 (7) 20/100 (8) 20/125 (9)	20/200 (10) or worse
20/25	20/25	20/30 (1) 20/40 (2) 20/50 (3)	20/60 (4) 20/70 (5) 20/80 (6) 20/100 (7) 20/125 (8)	20/200 (9) or worse
20/30	20/30	20/40 (1) 20/50 (2) 20/60 (3)	20/70 (4) 20/80 (5) 20/100 (6) 20/125 (7)	20/200 (8) or worse
20/40	20/40	20/50 (1) 20/60 (2) 20/70 (3)	20/80 (4) 20/100 (5) 20/125 (6)	20/200 (7) or worse
20/50	20/50	20/60 (1) 20/70 (2) 20/80 (3)	20/100 (4) 20/125 (5)	20/200 (6) or worse
20/60	20/60	20/70 (1) 20/80 (2) 20/100 (3)	20/125 (4)	20/200 (5) or worse
20/70	20/70	20/80 (1) 20/100 (2) 20/125 (3)	N/A	20/200 (4) or worse
20/80	20/80	20/100 (1) 20/125 (2)	N/A	20/200 (3) or worse
20/100	20/100	20/125 (1)	N/A	20/200 (2) or worse
20/125	20/125	N/A	N/A	20/200 (1) or worse
20/200	20/200	N/A	N/A	Worse than 20/200

\*Grade 1 is the same as screening (baseline) from a VA perspective. The Grade 1 Clinical Ocular AE will be an event when the AE is present (e.g., keratopathy) but there is no change in VA from baseline and the subject has little to no symptoms. If the AE is not treated aside from using artificial tears, then it would be considered Grade 1.

### **5.6.5.2.2 Ophthalmology Findings**

The ophthalmology report along with the completed study provided cover form will be forwarded to the Investigator in a timely manner. The investigator will review the ophthalmology report to guide further treatment decisions. The ophthalmologist and/or Medical Monitor will be consulted as indicated in Section [5.6.5.2.1](#)

The redacted ophthalmology report will also be forwarded to the Sponsor in a timely manner.

## **5.7 Adverse Events and Other Safety Aspects**

### **5.7.1 Definition of Adverse Events (AEs)**

An AE is defined as any untoward medical occurrence in a subject administered a study drug or has undergone study procedures and which does not necessarily have a causal relationship with this treatment. An AE can therefore be any unintended sign (including an abnormal laboratory finding), symptom, or disease temporally associated with the use of a medicinal (investigational) product, whether or not related to the medicinal (investigational) product.

This definition is broadened in this study to include any such occurrence (e.g., sign, symptom, or diagnosis) or worsening of pre-existing medical condition. Worsening indicates that the pre-existing medical condition has increased in severity, frequency, or duration of the condition or an association with significantly worse outcomes.

Interventions for pretreatment conditions (e.g., elective cosmetic surgery) or medical procedures that were planned before study enrollment are not considered AEs.

Some countries may have additional local requirements for events that are required to be reported as AEs or in an expedited manner similar to an SAE. In these cases, it is the investigator's responsibility to ensure these AEs or other reporting requirements are followed and the information is appropriately recorded in the eCRF accordingly.

An abnormality identified during a medical test (e.g., laboratory parameter, vital sign, ECG data, physical exam) should be defined as an AE only if the abnormality meets one of the following criteria:

- Induces clinical signs or symptoms
- Requires active intervention
- Requires interruption or discontinuation of study medication
- The abnormality or investigational value is clinically significant in the opinion of the investigator.

Disease progression should not be reported as an AE. Rather signs and symptoms associated with disease progression should be reported.

All AEs occurring after the first dose of investigational product observed by the investigator or reported by the subject (whether or not attributed to investigational product), will be reported in the eCRF. AEs will continue to be reported in the eCRF until 28 days post last dose, or at the subject's Safety Follow-Up visit, whichever occurs later. SAEs and medically significant AEs considered related to the investigational product by the investigator or the

Sponsor will be followed until resolved or considered stable. If a treatment-related adverse event is not resolved but is considered stable at the safety follow-up visit, this must be documented in the source documents.

The following attributes must be assigned by the investigator: description; dates of onset and resolution; severity; assessment of relatedness to investigational product, action taken, serious status and criteria.

It will be left to the investigator's clinical judgment whether or not an AE is of sufficient severity to require the subject's removal from treatment. However, the Medical Monitor will be consulted prior to the subject being discontinued from study for safety reasons.

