- b Non-clear cell subjects will sign at any time prior to screening for the main study. An immunohistochemical (IHC) H-score of ≥ 15 is required for non-clear cell subjects to qualify for study screening. IHC H-scores for ENPP3 eligibility do not expire for the duration of the study (i.e., there is no time limit from prescreen qualification to screening start).
- c Clear cell and IHC qualifying Non-clear cell subjects will sign ≤ 28 days of C1D1
- d Refer to Appendix [12.5](#)
- e At Screening, vitals will be taken once. Subjects randomized to AGS-16C3F, on the days of study drug administration, vital signs will be taken predose, and approximately 30 minutes after administration of study drug (i.e., end of infusion). Subjects randomized to axitinib, vital signs will be taken once at each clinic visit.
- f Laboratory assessments include hematology and chemistry (refer to Section [5.2.6](#)). All safety labs (all analytes listed in Section [5.6.3](#)) are performed locally. Starting from Cycle 5 Day 1 and for all subsequent cycles: A bone marrow study or hematology consult is strongly encouraged for all AGS-16C3F subjects whose predose platelet count is < 75 x 10^9/L at any 2 timepoints
- g To be performed ≤ 10 days of C1D1
- h All ECGs performed on study must be done in triplicate (3-5 min apart), and subjects must be in the same position for every reading. At Screening, ECGs will be taken in triplicate once. Subjects randomized to AGS-16C3F, at C1D1, ECGs will be taken predose (anytime predose on actual dosing day) and 2 hours after the end of infusion, when the total prescribed dose has been administered (e.g., 2 h after the end of infusion). Subjects randomized to axitinib, at C1D1, ECGs will be taken predose (anytime predose on actual dosing day) only. Refer to Section [5.6.4](#)
- i Women of childbearing potential only
- j All AEs and Concomitant Medications to be documented throughout the study.

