#### **3.2 Inclusion Criteria**

1. Is at least 18 years of age
2. Histologically confirmed diagnosis of RCC
  - a. Non-clear subjects must be ENPP3 positive, defined as IHC H-score  $\geq 15$
3. Has evidence of progression on or after the last regimen received:

- a. Clear cell subject: must have received at least 2 prior systemic regimens, one of which is an anti-VEGF agent.
  - b. Non-clear cell subject: must have received at least one prior anti-VEGF regimen
4. Has measurable disease according to Response Criteria for Solid Tumors (RECIST v.1.1)
5. Has ECOG Performance Status of 0 or 1
6. Has archive tumor tissue from primary tumor or metastatic site (excluding bone), for which the source and availability have been confirmed.
  - a. If no archive tissue is available, the subject may elect to have a biopsy performed to obtain tissue.
7. Has adequate organ function including:
  - a. Hematopoietic function as follows:
    - i. Absolute neutrophil count (ANC)  $\geq 1.5 \times 10^9/L$
    - ii. Platelet count  $\geq 100 \times 10^9/L$
    - iii. Hemoglobin  $\geq 9$  g/dL (transfusions are allowed)
  - b. Renal Function as follows:
    - i. Creatinine  $\leq 1.5 \times$  ULN, or calculated GFR  $> 40$  mL/min (Cockcroft-Gault) if creatinine  $> 1.5 \times$  ULN
  - c. Hepatic function, as follows:
    - i. Aspartate aminotransferase (AST) and Alanine aminotransferase (ALT)  $\leq 2.5 \times$  ULN or  $\leq 5 \times$  ULN if known liver metastases
    - ii. Total bilirubin  $\leq 1.5 \times$  ULN
8. Prothrombin time (PT) and activated partial thromboplastin time (aPTT) levels  $\leq 1.5 \times$  ULN. If institution does not report PT value, the INR must be  $\leq$  ULN
  - a. If subject is receiving Coumadin (warfarin), a stable international normalization ratio (INR) of 2-3 is required.
9. No clinical symptoms of hypothyroidism
10. Urine Protein to Creatinine Ratio (uPCR)  $< 2.0$ 
  - a. If uPCR  $\geq 2.0$  then a 24-hour urine collection can be performed to qualify. If this is performed to qualify, the protein result must be  $< 2$  g per 24 hours.
11. Female subject must either:
  - a. Be of non-childbearing potential:
    - i. post-menopausal (defined as at least 1 year without any menses) prior to Screening, or
    - ii. documented surgically sterile

- b. Or, if of childbearing potential,
  - i. Agree not to try to become pregnant during the study and for 6 months after the final study drug administration

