### 5.7.5 Reporting Procedures for All Serious Adverse Events (SAEs)

All SAEs occurring after the first dose of investigational product observed by the investigator or reported by the subject (whether or not attributed to investigational product), will be reported to the sponsor. SAEs considered related to the investigational product by the investigator or the Sponsor will be followed until resolved or considered stable.

All SAEs that occur up to the last formal follow-up observational period, must be reported  $\leq 1$  working day of discovery or notification of the event.

In the case of a SAE, the investigator must contact the sponsor by fax or email immediately (within 24 hours of awareness).

The investigator must complete and submit a SAE worksheet containing all information that is required by local and/or regional regulations to the sponsor by email or fax immediately (within 24 hours of awareness).

For contact details, see [Section II Contact Details of Key Sponsor's Personnel](#). Fax or email the SAE Worksheet to:

Astellas Pharma Global Development, Inc.  
Pharmacovigilance  
[contact]  
Alternate North America [contact]  
Email: [[contact]](mailto:[contact])

The investigator should notify the IRB/IEC/REB of SAEs occurring at the site and other AE reports received from Sponsor, in accordance with local requirements and procedures.

If there are any questions, or if clarification is needed regarding the SAE, please contact the Sponsor's Medical Monitor/Expert or his/her designee (see [Section II Contact Details of Key Sponsor's Personnel](#)).

The SAE form should be completed with all available information but at the very bare minimum the following information is required for a case to be valid:

- Identifiable subject (Subject number)
- Identifiable reporter (e.g., investigator)
- A description of the SAE, and
- Suspect drug

In addition to the above 4 critical information to establish a valid case, the following information is needed to assess the regulatory reporting requirement and Sponsor's causal attribution:

- Causality
- Event description
- Event onset date
- Study drug treatment dates

Post initial SAE report submission, the investigator will promptly submit any relevant information that becomes available (e.g., information that impacts causality, changes event outcome, changes event severity).

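### AE and SAE reporting starts at first dose although the AE definition covers study procedures, so a complication of a qualifying biopsy that begins before dosing need not be reported

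*Protocol*

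**What the plan says.** Protocol 5.7.1 defines an AE as "any untoward medical occurrence in a subject administered a study drug or has undergone study procedures". Being dosed is therefore not a condition for having an AE.

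The reporting rules start later. Section 5.7.1 sends to the eCRF "All AEs occurring after the first dose of investigational product observed by the investigator or reported by the subject". Section 5.7.5 sends to the sponsor "All SAEs occurring after the first dose of investigational product observed by the investigator or reported by the subject". Footnote j of Table 1 says "All AEs and Concomitant Medications to be documented throughout the study" but names no starting point.

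Inclusion criterion 6 in Protocol 3.2 requires tumor tissue and adds at 6a: "If no archive tissue is available, the subject may elect to have a biopsy performed to obtain tissue". For non-clear cell subjects, Protocol 5.2.2 places tissue collection under a separate prescreening consent, before main screening. Protocol 5.2.1 sets no time limit between prescreen qualification and the start of screening. The main consent and the screening procedures fall within 28 days of C1D1.

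**The concern.** The protocol asks some patients to accept an invasive procedure in order to qualify, and its AE definition acknowledges that procedures can cause AEs. The duty to report then begins only after those procedures are over. A serious bleed or infection after a qualifying biopsy, including one that prevents the patient from being dosed, lies outside the stated SAE rule.

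What is at stake is subject protection and the sponsor's view of its own entry procedures. The efficacy result is not at stake. The people least visible are those who never receive study drug: patients who fail the H-score threshold, patients who fail screening, and subjects randomized but not dosed. The safety analysis set in both documents requires at least one dose, and SAP 19 bases every safety output on that set.

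**Working it through.** The documents give no figure for this point, so the check is mainly a comparison of passages.

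**1. Definition against window.** The definition (5.7.1) needs a study procedure or a dose. The windows (5.7.1 and 5.7.5) need a first dose. An event that satisfies the first and precedes the second is an AE by definition but has no reporting duty.

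**2. What precedes first dose.**
- Tissue for non-clear cell subjects, obtained under the prescreening consent (5.2.2).
- A biopsy done to meet Inclusion 6a (3.2).
- Screening imaging and the dilated eye exam (5.2.3, 5.6.5).
- In the AGS-16C3F arm, the required prednisolone drops that begin on Day -1 (5.1.3.1).

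**3. Length of the gap.** It is up to 28 days for main screening, which includes the at most 5 days from randomization to treatment (4.4). It is open-ended for prescreening, and it is the whole period for anyone never dosed.

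**4. Other routes by which the event might be recorded.**
- Medical history (5.3.2) covers conditions up to randomization, and SAP 12 covers conditions that start before first dose and end on or before it.
- Medications and treatments are recorded from consent signature (5.1.3).
- SAP 19.1 lists non-TEAEs, and SAP Appendix 2 handles AE start dates before first dose. The protocol does not require sites to enter such events.
- A pre-dose condition that worsens after first dose is a reportable AE under the broadened definition in 5.7.1.

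The history and treatment records carry no seriousness, causality or expedited report. Section 5.7.1 asks for relatedness to the investigational product and does not mention procedures. Failure to report would not be a notifiable deviation either, because Protocol 8.1.6 refers to SAEs not reported as the protocol defines, and that definition begins at first dose.

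**5. Table 1.** The AE row, as far as the table can be read, has no mark under Screen. The concomitant medication row shares that layout and footnote j, yet 5.1.3 opens its window at consent. The table therefore does not settle where AE documentation starts.

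**6. Size.** The share of subjects without archive tissue is not stated; assume 5% to 20%. Only non-clear cell subjects must supply tissue before screening, and Protocol 2.2.3 caps them at 26:

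- 26 × 0.05 = 1.3
- 26 × 0.20 = 5.2

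That is about 1 to 5 randomized subjects. Prescreen and screen failures come on top, in a number the documents do not give. Clear cell subjects cannot be counted. Table 1 lets them supply tissue at any time on study, and 5.2.1 asks for submission within 3 months of consent, so a biopsy may follow dosing. Yet 5.2.1 also requires archive availability to be confirmed for eligibility, which leaves the timing unclear for those who have none.

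**The case against.** The strongest reply is that a definition says what an AE is and a window says when it is collected. A window narrower than the definition is not in itself a contradiction, and the procedures wording still has work to do on treatment (PK draws, eye exams, on-study biopsies). That is fair, and footnote j can be read in agreement with 5.7.1. A reader might infer that three passages flatly contradict one another. The documents do not go that far, because footnote j gives no start date. What stands is that no passage opens AE or SAE reporting before first dose.

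A reader might also infer that pre-dose harm is never captured. That is too strong. A complication that begins after first dose is reportable whatever its cause. The routes in step 4 may leave a trace in randomized subjects, their reasons for discontinuation are tabulated, and a death counts in overall survival. Local reporting and ethics-board duties in 5.7.1 and 5.7.5 also remain, although they depend on the jurisdiction and are not a study rule. None of these replaces an SAE report.

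Applying the assumed 5-20% to all 134 subjects would give 134 × 0.05 = 6.7 to 134 × 0.20 = 26.8, or 7 to 27. The documents do not support that as an estimate, because clear cell tissue may be supplied after dosing.

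Two further points limit the weight. The IDMC charter and its list of outputs are separate documents, so what the IDMC actually sees cannot be fully judged. And Version 6.0 is dated 12 August 2020, with a planned study end of 3Q2020. Enrolment closure is not stated, but a new screening rule may have little left to catch. Section 5.7.1 also excludes procedures planned before enrolment from being AEs; that covers the procedure and does not clearly cover its complications.

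**Conclusion.** The concern holds in this form: a complication of a study-mandated procedure that begins before first dose need not be reported as an AE or SAE, although the protocol's definition includes it. The gap is partial in randomized subjects, where history or treatment records may show something. For prescreen and screen failures the documents state no route at all.

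The plausible size is about 1 to 5 randomized non-clear cell subjects having a qualifying biopsy, plus failures and an unknown number of clear cell subjects. This counts biopsies, not complications, and rests wholly on the assumed 5-20% without archive tissue. The primary PFS analysis and the TEAE tables do not change. It is a safety-reporting gap that is small in expected numbers and cheap to close.

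**What to change.** In Protocol 5.7.1 and 5.7.5, state that SAEs related to study-mandated procedures are reported from signature of the first consent (prescreening or main), and that all AEs are reported from first dose. Align the AE row and footnote j of Table 1 with that rule, and have the SAE worksheet record relatedness to a procedure. List pre-dose events separately, including those in subjects never dosed. SAP 19.1 already lists non-TEAEs, and the TEAE definition and tables stay as they are.

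If enrolment has already closed, ask sites whether any procedure-related SAE occurred before dosing, including in prescreen and screen failures, and state the limitation in the CSR.

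The cost is a sentence or two in the protocol and SAE instructions and a few extra SAE reports, or one round of site queries.

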### **5.7.2 Definition of Serious Adverse Events (SAEs)**

An AE is considered "serious" if, in the view of either the investigator or Sponsor, it results in any of the following outcomes:

- Results in death
- Is life threatening (an AE is considered "life-threatening" if, in the view of either the investigator or Sponsor, its occurrence places the subject at immediate risk of death. It does not include an AE that, had it occurred in a more severe form, might have caused death)
- Results in persistent or significant disability/incapacity or substantial disruption of the ability to conduct normal life functions
- Results in congenital anomaly, or birth defect
- Requires inpatient hospitalization or leads to prolongation of hospitalization (hospitalization for treatment/observation/examination caused by AE is to be considered as serious)
- Other medically important events

Medical and scientific judgment should be exercised in deciding whether expedited reporting is appropriate in other situations, such as important medical events that may not be immediately life-threatening or result in death or hospitalization but may jeopardize the subject or may require intervention to prevent one of the other outcomes listed in the definition above. These events, including those that may result in disability/incapacity, should also usually be considered serious. Examples of such events are intensive treatment in an emergency room or at home for allergic bronchospasm; blood dyscrasias or convulsions that do not result in hospitalization; or development of drug dependency or drug abuse.

Safety events of interest on the medicinal products administered to the subject as part of the study (e.g., study drug, comparator, background therapy) that may require expedited reporting and/or safety evaluation include, but are not limited to:

- Overdose of the medicinal product(s)
- Suspected abuse/misuse of the medicinal product(s)
- Inadvertent or accidental exposure to the medicinal product(s)

Medication error involving the medicinal product(s) (with or without subject exposure to the Sponsor medicinal product, e.g., name confusion)

### 5.7.3 Criteria for Causal Relationship to the Study Drug

AEs that fall under either "Possible" or "Probable" should be defined as "AEs whose relationship to the study drugs could not be ruled out".

Causal relationship to the study drug	Criteria for causal relationship
Not Related	A clinical event, including laboratory test abnormality, with a temporal relationship to drug administration which makes a causal relationship improbable, and/or in which other drugs, chemicals or underlying disease provide plausible explanations.
Possible	A clinical event, including laboratory test abnormality, with a reasonable time sequence to administration of the drug, but which could also be explained by concurrent disease or other drugs or chemicals. Information on drug withdrawal may be lacking or unclear.
Probable	A clinical event, including laboratory test abnormality, with a reasonable time sequence to administration of the drug, unlikely to be attributed to concurrent disease or other drugs or chemicals, and which follows a clinically reasonable response on re- administration (rechallenge) or withdrawal (dechallenge).

